Official Title: Evaluation of Bioness Integrated Therapy System (BITS) Touch Screen Technology to
Improve Field Awareness

Clinical Trial Number: NCT04930822

Study Closeout: June 27, 2025

STUDY PROTOCOL AND STATISTICAL ANALYSIS PLAN

Methods

Research design: Unblinded randomized control trial

Patient Population/Enrollment Criteria: Individuals enrolled in this study must meet the following criteria:

1. Individuals enrolled in this study must meet the following criteria:
 - ii. Adults, 18 years or older who are able to provide consent or have Power of Attorney (POA) able to consent.
 - iii. Must have an acute or subacute (diagnosed within the last 3 months) neurological diagnosis with a visual field deficit as verified by occupational therapist via confrontation testing.
 - iv. Admitted into Gaylord Hospital, a long term acute care hospital
 - v. Demonstrate the ability to follow 1 step directions
 - vi. Demonstrate sufficient upper extremity strength (as deemed appropriate by occupational therapist) to utilize BITS touch screen technology
 - vii. Ability to tolerate at least 30 minutes of intervention at a seated wheelchair level.

1. Exclusion Criteria:

1. Severe cognitive impairments: Unable to follow one step directions, inability to communicate pain, or to stop intervention if needed
2. Quadriplegia
3. Previous significant visual impairment impacting visual fields or resulting in legal blindness in past medical history
4. Re-admitted to Acute Care and do not return within 1 week
5. Currently on a ventilator for respiratory support
6. Unstable vital signs or deemed inappropriate to participate in therapy per RN/MD
7. Uncontrolled or new (within 24 hours) arrhythmias.
8. Unresolved or new (within 24 hours) deep vein thrombosis.
9. Concurrent severe neurological pathology/disease or stroke within 72 hours.
10. Any reason the physician may deem as harmful to the participant to enroll or continue in the study.

A total of at least 30 adult Participants meeting these criteria will be included. This will include 15 participants in "A" Group and 15 participants in "B" Group. There will be no upper age limitation.

Equipment and Intervention: Used for this study was the Bioness Integrated Therapy System (BITS[®]) (Valencia, CA) with 55-inch display.¹ As participants were consented and enrolled, they were alternately assigned to either the control group or the experimental group using the BITS. Over three-weeks, both groups received six, 20 minute long, vision-specific treatment sessions. The control group completed conventional table-top and pen and paper exercises, while the experimental group completed gamified, technology-assisted versions of similar exercises. Outside of these sessions, participants completed a standard rehabilitation regimen consisting of

three hours of daily comprehensive therapy (i.e., physical, occupational, speech, etc.) as prescribed by their treating physician.

Subject Assignment: Participants will be screened through an electronic report extracted from the electronic medical record. This will include all patients admitted under the stroke and traumatic brain injury (TBI) programs who have documentation supporting visual field impairments in the initial occupational therapy evaluation. Once they have been screened and all inclusion/exclusion criteria have been reviewed, patients will be consented to participate in the study and randomly assigned to "A" and "B" group in alternating fashion. If a participant exits the study before completion, their spot in the intervention will be replaced by a new participant.

Study Timeline: The enrollment period commences after the IRB has approved the study and the study initiation visit has been conducted. The enrollment and data collection periods are expected to last 12 months to obtain 30 participants. The goal is to have participants participate in scheduled occupational therapy sessions lasting a minimum of 20 but no more than 30 minutes for a total of six sessions focusing on vision therapy vs BITS training.

Outcome Measures and Data Collection: The primary outcome measures included the Bells Test, conducted by an occupational therapy practitioner involved in the study, and Kinetic Visual Field testing, conducted by a licensed neuro-optometrist.² Bells and Kinetic Visual Field Testing were completed at baseline and again following the six study sessions.

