Data Analysis: Data was analyzed using GraphPad Prism version 10.3.1 (GraphPad Software, San Diego, CA). A complete case analysis approach was used. Descriptive statistics and 95% confidence intervals were used to describe population characteristics. All data sets were analyzed for normality to evaluate if there were violations in the equal variances assumptions between groups. Nonparametric testing was used as necessary following the results of testing. Age data demonstrated normal distribution with comparable variance and was analyzed using an unpaired t-test. Length of stay (LOS) data demonstrated non-normal distribution and was analyzed using Mann-Whitney-U Rank sum test. Demographic characteristics were analyzed using Chi-Square (χ^2). To assess for within and between group differences, a two-way repeated measures analysis of variance (ANOVA) with post-hoc uncorrected Fisher's least significant difference (LSD) multiple comparison test was completed. Statistical significance was set at an alpha level of 0.05 for all statistical tests.

References:

1. BITS - Bioness [Internet]. [cited 2025 Nov 13]. Available from: <https://bionessmedical.com/bits/>
2. Bells Test – Strokengine [Internet]. [cited 2025 Nov 13]. Available from: <https://strokengine.ca/en/assessments/bells-test/>

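### Time since diagnosis may vary up to 3 months at entry, yet it is neither compared between arms nor in the model; the cost is precision and interpretability, not a raised false-positive rate

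*Combined protocol and SAP*

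**What the plan says.** All of this is in the combined protocol and SAP.

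- **Entry window** (Patient Population/Enrollment Criteria): "Must have an acute or subacute (diagnosed within the last 3 months) neurological diagnosis". The only early limit in the text is an exclusion tied to stroke: "Concurrent severe neurological pathology/disease or stroke within 72 hours". No minimum time is given for other diagnoses.
- **Case mix** (Subject Assignment): screening covers "all patients admitted under the stroke and traumatic brain injury (TBI) programs" with a documented field impairment.
- **Size** (Patient Population/Enrollment Criteria): "A total of at least 30 adult Participants meeting these criteria will be included", 15 in each group.
- **Assignment** (Equipment and Intervention): "they were alternately assigned to either the control group or the experimental group using the BITS". No stratification or minimisation factor is named. Under Subject Assignment, if someone leaves early, "their spot in the intervention will be replaced by a new participant".
- **Follow-up** (Equipment and Intervention; Outcome Measures and Data Collection): six sessions over three weeks, with both primary outcomes measured before and after. Both arms also receive three hours of general therapy a day.
- **Analysis** (Data Analysis): "a two-way repeated measures analysis of variance (ANOVA) with post-hoc uncorrected Fisher's least significant difference (LSD) multiple comparison test was completed". No covariate is named. The arms are compared on age (t-test), length of stay (Mann-Whitney) and unlisted demographic characteristics (chi-square).

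Time since diagnosis appears only as an eligibility criterion.

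**The concern.** If natural recovery slows with time, someone who enters soon after diagnosis can expect more change over three weeks than someone who enters near the 3-month limit, whichever arm they are in. With two groups and two time points, the group-by-time test in the ANOVA is equivalent to a t-test on change scores. It removes each participant's starting level. It does not remove a rate of change that depends on recovery stage, which goes straight into the change score.

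This has two consequences. The spread in natural recovery adds to the error of the comparison. And if one arm of 15 happens to hold more early entrants, part of the observed difference (or of its absence) reflects recovery stage. A reader could not detect this, because the distribution of time since diagnosis by arm is not among the planned comparisons. Length of stay is not a substitute, since it does not measure time from diagnosis to baseline.

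**Working it through.** **The plan's own figure.** The sample size of 30 comes with no effect size, SD or power, so it cannot be reproduced. For scale, the effect detectable with 80% power at two-sided 0.05 (sidedness assumed) with 15 per arm is (1.960 + 0.842) × √(2/15) = 1.02 SD by normal approximation. Power is about 59% for 0.8 SD and 28% for 0.5 SD.

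**Inputs.** From the documents: 15 per arm, an upper limit of 3 months, and follow-up of three weeks (21 days). Assumed: uniform entry over days 4-90 (wide) or days 14-60 (narrow), and exponential recovery with time constant τ of 20, 30 or 45 days.

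**Step 1: chance gap in mean time since diagnosis.** SD = (width of window)/√12, and the 95% gap is 1.96 × SD × √(2/15).

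- Days 4-90: SD = 86/√12 = 24.8; gap = 1.96 × 24.8 × 0.365 = 17.8 days.
- Days 14-60: SD = 46/√12 = 13.3; gap = 1.96 × 13.3 × 0.365 = 9.5 days.

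**Step 2: natural gain in three weeks.** As a fraction of the deficit recoverable at diagnosis, f(t) = exp(−t/τ) × (1 − exp(−21/τ)). The 95% chance arm difference is 1.96 × SD(f) × √(2/15), with SD(f) taken over the entry window.

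| τ (days) | f at day 4 | f at day 90 | SD(f), 4-90 | 95% difference, 4-90 | SD(f), 14-60 | 95% difference, 14-60 |
|---|---|---|---|---|---|---|
| 20 | 0.53 | 0.007 | 0.134 | 9.6% | 0.080 | 5.8% |
| 30 | 0.44 | 0.025 | 0.113 | 8.1% | 0.070 | 5.0% |
| 45 | 0.34 | 0.050 | 0.082 | 5.8% | 0.050 | 3.6% |

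The range is therefore about 4-10% of the recoverable deficit.

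**Step 3: precision.** Simulated change = (recoverable points) × f(t) + effect × arm + normal error, 15 per arm, 20,000 trials per row. It was analysed by least squares on arm, with and without log(days).

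| Entry days | Recoverable points | τ | Residual SD = true effect | Power without | Power with log(days) |
|---|---|---|---|---|---|
| 4-90 | 20 | 30 | 4 | 63% | 74% |
| 4-90 | 20 | 30 | 5 | 68% | 74% |
| 4-90 | 20 | 45 | 5 | 71% | 74% |
| 4-90 | 10 | 30 | 4 | 72% | 73% |
| 14-60 | 20 | 30 | 4 | 71% | 74% |
| 14-60 | 10 | 30 | 4 | 75% | 74% |
| 14-60 | 10 | 30 | 5 | 75% | 74% |

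In the first row the standard error falls from 1.66 to 1.48. In the last two rows the covariate gains nothing.

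**Step 4: type I error.** With the first row's settings and no true effect, rejection is about 5% with and without log(days). A separate simulation with entry uniform over days 3-91 looked only at trials whose arms differ by more than 0.5 SD in mean time since diagnosis (about 17% of trials). Unadjusted rejection there was 0.07, 0.11 and 0.18 for correlations of 0.3, 0.5 and 0.7 between time and change, and about 0.05 after adjustment.

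To place step 3 on that scale, the share of change variance due to natural recovery is (points × SD(f))² / [(points × SD(f))² + residual SD²].

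- First row: 2.26²/(2.26² + 4²) = 0.24, a correlation of about 0.49.
- Narrow window, 10 points, SD 4: 0.70²/(0.70² + 4²) = 0.03, about 0.17.

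The 0.18 figure thus needs a stronger link than any row in step 3.

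**The case against.** The strongest reply is that the unadjusted test already allows for chance imbalance. That is right, and it limits the point. A reader might infer from the wide window that the trial is biased or that its false-positive rate is raised. The documents do not support this. When assignment is unrelated to prognosis, the imbalance averages out over repetitions and is counted in the standard error (step 4). Alternation is predictable, so that condition is not guaranteed, but nothing in the documents shows that it failed.

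The second reply is that the real window may be narrower. Participants must be inpatients of a long-term acute care hospital, be off the ventilator, tolerate half an hour of seated treatment and have had an occupational therapy evaluation. Very early entry may be uncommon. The 72-hour criterion sits among exclusions for acute instability and is not clearly a lower entry limit. This stands, which is why days 14-60 are shown beside days 4-90. It is also tempting to quote only the 10-point power gain, but that row assumes 20 recoverable points for everyone, or 57% of the 35-point Bells scale (20/35). With 10 points and the narrow window the gain is nil.

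The third reply is that diagnosis type or initial severity could be argued for equally. In part this stands. Time since diagnosis has the practical advantage that it must already be known to apply the eligibility criterion, and the baseline value in the proposed model covers severity in part.

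**Conclusion.** The omission is real and modest. The plan admits participants over a span in which natural recovery may differ, then neither describes nor models where each one stands in it. The harm is some lost precision and a result that cannot be interpreted with confidence if the arms happen to differ in recovery stage. Under the assumed curves, chance alone can separate the arms by about 4-10% of the recoverable deficit (95% range), and the power recoverable by adjustment runs from about none to about 10 percentage points. The absence of a term for time since diagnosis and of a named baseline comparison is plain from the text. The sizes rest wholly on assumed entry distributions, recovery curves, recoverable points and residual SDs, because the documents give none of these.

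**What to change.** 1. Take days from diagnosis to baseline testing from the medical record already used for screening.
2. Report this by arm (median, quartiles, range) beside age and length of stay.
3. Make the between-arm comparison of each primary outcome a linear model of the post-test value on arm, baseline value and days since diagnosis, for example on a log scale. The log form is a convenience; the documents give no basis for one shape over another.
4. Closeout is dated June 27, 2025, and the Data Analysis text describes completed work. An adjusted analysis added now should be labelled post hoc and shown beside the original ANOVA.

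The cost is one date per participant and one or two degrees of freedom: the change-score comparison has 30 − 2 = 28, and the model with baseline and days has 30 − 4 = 26. If the real entry window is narrow, expect little or no gain in precision. The power figures above are for adding log(days) to a model of change; the further effect of moving to a post-test model with baseline as covariate was not estimated. Item 2 is worth doing whatever the window, since it lets a reader see whether the arms were comparable.

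### The trial is labelled randomized, but allocation is described as alternation with no concealment described, so after the first participant each arm is predictable and the comparison is open to selection bias

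*Combined protocol and SAP*

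**What the plan says.** The combined protocol and SAP addresses allocation in three places.

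- Methods, design line: "Research design: Unblinded randomized control trial".
- Methods, Equipment and Intervention: "As participants were consented and enrolled, they were alternately assigned to either the control group or the experimental group using the BITS".
- Methods, Subject Assignment: after screening and consent, patients are said to be randomly assigned to the A or B "group in alternating fashion".

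The same paragraph covers withdrawals: "If a participant exits the study before completion, their spot in the intervention will be replaced by a new participant". It does not say which arm the replacement joins, although the wording suggests the vacated one.

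The sample is at least 30, with 15 per group. Eligibility includes judgements by staff: the occupational therapist decides whether upper-extremity strength is adequate, and the last exclusion criterion is "Any reason the physician may deem as harmful to the participant to enroll or continue in the study". Screening uses an electronic report, described with "This will include all patients admitted under the stroke and traumatic brain injury (TBI) programs", restricted to those whose initial occupational therapy evaluation documents a visual field impairment.

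The document mentions no random list, blocks, envelopes, central system or independent allocator. It does not say how the first arm was chosen, who enrolled participants, or who could see the running order.

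**The concern.** Alternation is a deterministic rule. The most that *randomly* could mean alongside it is a random choice of the first arm; from then on each assignment follows from the one before. Concealment could not protect such a sequence, because the last assignment reveals the next. The last assignment is easy to know here: the trial is unblinded, and a 55-inch touch screen is not mistaken for table-top exercises.

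Screening, eligibility review and consent all come before assignment, when the next arm can already be inferred. Someone who knows it can enrol a patient now or wait, and the discretionary criteria leave room to do so without breaking a rule. In a trial this small, repeated decisions of that kind can make the groups differ in prognosis before treatment starts. The planned p-values can still be computed, but a between-group difference could not be attributed to BITS with the confidence that the word *randomized* invites. The document states no such limitation.

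**Working it through.** **Label against method.** The design line says randomized. One allocation statement says alternation only; the other says random and alternating together, which is self-contradictory unless only the start was random. No passage supplies a random sequence that would reconcile them.

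**Predictability.** The plan's sample size is consistent with alternation: 15 + 15 = 30. With exactly 30 assignments and no replacements, all but the first are determined, so 29 of 30 are known in advance. If the first is a coin toss, the expected share guessed correctly is (29 + 0.5)/30 = 98.3%. For comparison, by simulation with past allocations visible, the share is about 70% for random permuted blocks of 2, 4 and 6 and 50% for simple randomization. A replacement does not restore unpredictability: if it takes the vacated spot its arm is known, and if it joins the end of the queue alternation gives its arm.

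**Possible size of the effect.** The document gives no information on steering, so every input here except 15 per arm and alpha 0.05 is an assumption. Prognosis is standard normal, there is no device effect, and tests are two-sided. The first slot is unsteered and the other 29 can be steered. A worse-than-median candidate for a BITS slot, or a better-than-median one for a control slot, is deferred with probability q.

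- Unfavourable share among those enrolled in steered slots: (1 − q)/(2 − q).
- Expected deferrals over the trial: 29 × q/(2 − q).
- Expected between-arm shift: 2 × 0.798 × q/(2 − q) × 29/30 × r SD. Here 0.798 = √(2/π) is the mean of the upper half of a standard normal, and r is the correlation of prognosis with outcome. For q = 0.25 and r = 1: 2 × 0.798 × 0.143 × 0.967 = 0.22 SD.

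| q | Unfavourable share | Expected deferrals | Shift, r = 0.7 to 1.0 |
|---|---|---|---|
| 0.10 | 0.474 | 1.5 | 0.06-0.08 SD |
| 0.25 | 0.429 | 4.1 | 0.15-0.22 SD |
| 0.50 | 0.333 | 9.7 | 0.36-0.51 SD |

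Simulated type I error (60,000 runs per setting; with q = 0 it is 4.9-5.2%):

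| Analysis | q = 0.10 | q = 0.25 | q = 0.50 |
|---|---|---|---|
| t-test on post score, r = 0.7 to 1.0 | 5-6% | 7-9% | 17-30% |
| Group-by-time, steering on baseline severity | 5% | 5-6% | 6-11% |
| Group-by-time, steering on recovery potential | 5-6% | 7-9% | 13-29% |
| Baseline-adjusted, steering on baseline severity | 5% | 5% | 5% |
| Baseline-adjusted, steering on recovery potential | 5-6% | 7-9% | 16-30% |

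The group-by-time rows refer to the planned two-way repeated measures ANOVA. With two groups and two time points that term is equivalent to a t-test on change, run here with baseline-post correlations of 0.5 to 0.9. Steering on baseline severity then shifts the change score against BITS, because the better-starting group gains less.

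**Dependence on the model.** A harsher rule, in which the enroller moves the next patient's expected outcome by ±0.1, ±0.25 or ±0.5 SD according to the predicted arm, gives biases of about 0.19, 0.50 and 0.98 SD and type I errors of about 7.7%, 26% and 73% (5,000 runs). With permuted blocks of 2, 4 and 6 and past allocations visible, the same rule gives about 5.4%, 7.5% and 17%.

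**The case against.** The strongest reply is that alternation and lack of blinding are openly disclosed, no steering is shown, and the simulated sizes come entirely from assumptions. That is right about the sizes. About four deferrals in the whole trial give only 0.15-0.22 SD and 7-9%; the 17-30% range needs about ten among roughly 40 candidates, and its top end assumes that staff judge outcome-relevant prognosis perfectly. The 29-of-30 count itself assumes exactly 30 participants and no replacements.

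Other points also stand in part. The absence of concealment is an absence from the text, not proof that nothing was done. The physician exclusion is limited to harm to the participant, so it is less open-ended than a bare reference to physician discretion suggests. Screening from an electronic report narrows the pool using a record made before consent, which limits the risk. The plan already compares age, length of stay and demographics, and the planned ANOVA could supply a baseline contrast on the outcomes. A baseline-adjusted analysis added now would be post hoc and would not repair steering on unmeasured prognosis.

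None of this removes the contradiction. Disclosing alternation in one paragraph does not make the randomized label correct, and a screening report does not hide the next arm.

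**Conclusion.** The concern holds. As written, the document claims randomization and describes alternation. That conclusion rests on the text alone and needs no simulation; it would change only if a random list was in fact used and left undescribed. The firm figure is 29 predictable assignments of 30 under strict alternation.

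The consequence is a risk, not a demonstrated bias. Under the main deferral model it runs from close to nothing at 10% deferral to a type I error of up to about 30% at 50% deferral, and the planned ANOVA is affected most if steering follows recovery potential. The correction is essential because readers will weigh between-group tests at alpha 0.05 as randomized evidence. The extra analysis is secondary.

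**What to change.** The title block gives "Study Closeout: June 27, 2025", so allocation cannot be changed and the main correction is to the wording.

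1. In the design line, replace the randomized label with *controlled trial with alternating (quasi-randomized) allocation*, keeping *unblinded*. In Subject Assignment, say *assigned by alternation*. If a random list was used, describe how it was generated and concealed, and delete the alternation wording instead.
2. State the selection-bias limitation wherever between-group conclusions are drawn.
3. Report how the first arm was chosen, who enrolled participants, whether they knew the next arm, how replacements were assigned, and the numbers screened, eligible, declined and enrolled.
4. Compare baseline Bells and visual field scores by arm and add a baseline-adjusted sensitivity analysis. Label it post hoc, and say that it does not remove bias from unmeasured prognosis. Because each eye is scored separately, either use one visual field score per participant or account for the pairing of eyes.

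Only if further participants are enrolled: use a concealed computer-generated list in permuted blocks of varying size, opened after consent and baseline testing, with replacements taking the next number.

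The cost is a few sentences, one analysis on scores already collected (one degree of freedom with one score per participant) and retrieval of screening counts if they were kept. The real price is a less favourable design label.
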